1 PROTOCOL SUMMARY

1.1 SYNOPSIS

Title:	Strengthening Adolescent-Adult Networks to Reduce Youth Violence
Grant Number:	1K23HD098277-01
Study Description:	This community-partnered cluster-randomized trial will examine the feasibility and acceptability of a social network-based youth violence prevention program called Strengthening Connections for Change for youth ages 13-17 and their key adult supports. Set in four lower resource Pittsburgh, Pennsylvania neighborhoods, this study brings together youth ages 13-17 and their self-identified key adult supports to focus on leadership, strengthening intergenerational networks, community engagement, and violence prevention.
Objectives[*]:	The primary goal is to test the feasibility and acceptability of the adapted Youth Empowerment Solutions intervention (Strengthening Connections for Change, SCC) compared to a control intervention (Job Skills) delivered over 12 weekly sessions through a cluster-randomized community-based trial among adolescents, ages 13- 17 (n=50 youth, 25 in intervention group and 25 in control group) and their key adult supports (n=25 in intervention group) at four community-based sites (2 intervention and 2 control sites) in Pittsburgh, PA. As this is a feasibility trial, the primary end points are feasibility and acceptability.
Endpoints[*]:	Primary outcomes will include feasibility and acceptability. Feasibility is defined by participant attendance calculated as a proportion of total number of sessions attended (possible session attended #: 0-12 for youth participants and 0-9 for adult participants; possible proportion attended range: 0-1). Acceptability is defined as overall satisfaction with curriculum content and format among youth (intervention and control) and among adults (intervention) measured at the end of programming. Secondary outcome measures include assessment of participant satisfaction on weekly session feedback forms. Exploratory outcomes include changes between pre-and post-intervention assessments of social network-level measures (e.g., network size, network density, mean link strength), attitudes towards violence, conflict resolution and coping, future orientation, and violence experiences.
Study Population:	Youth between the ages of 13 and 17 who live or attend programming within randomized neighborhood boundaries and their self-identified key adult supports.
Phase[*] or Stage:	N/A

**Description of
Sites/Facilities Enrolling
Participants:**

The trial will be conducted in partnership with youth-serving community organizations in each neighborhood. Programming will be delivered in community settings and overseen by the Division of Adolescent Medicine research team.

**Description of Study
Intervention/Experimental
Manipulation:**

Strengthening Connections for Change is a 12-session curriculum adapted from the Youth Empowerment Solutions (YES) program and designed to strengthen adolescent-adult support networks, build leadership skills, foster community engagement, and challenge attitudes and behaviors that foster violence involvement. During the program, youth ages 13-17 years invite their self-identified key adult supports to jointly participate in programming including youth-focused, adult-focused and jointly focused activities. Towards the end of programming participants design a community project to strengthen intergenerational connections and promote community engagement.

[figure not shown]
Study Duration ^{*}:

15 months

Participant Duration:

12 weeks

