3 OBJECTIVES AND ENDPOINTS

OBJECTIVES	ENDPOINTS	JUSTIFICATION FOR ENDPOINTS	
Primary	
The primary goal of the study is to pilot test the feasibility and acceptability of the adapted Youth Empowerment Solutions intervention (Strengthening Connections for Change) compared to a control intervention (Job Skills).
	
Primary outcomes will include feasibility and acceptability. Feasibility is defined by session attendance. Attendance will be recorded at the beginning and end of each session. Attendance will be calculated as a proportion of total number of sessions attended (possible session attended #: 0-12 for youth participants and 0-9 for adult participants; possible proportion attended range: 0-1). Feasibility is defined by participant satisfaction. Participant Overall Satisfaction with Curriculum Content and Format will be assessed by researcher-generated Likert-scale items. At the end of the program, participants will be asked about how satisfied they were overall with the topics discussed and format of the program using 5-point Likert scale items. Means score will be calculated across the items (possible range: 1-5; higher score means higher satisfaction).
	
Feasibility and acceptability are crucial to assess before planning a larger efficacy trial because if the program is not feasible or acceptable, changes will need to be made prior to a large-scale RCT. Moreover, satisfaction is an important indicator of overall interest in the intervention, and whether youth found this programming engaging and relevant.
 
Operationalizing feasibility and acceptability came from stakeholder meetings about the amount of the curriculum that participants should receive to consider their participation as meaningful engagement.

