4.4 END-OF-STUDY DEFINITION

A participant is considered to have completed the study if he or she (1) completes the baseline survey, (2) attends either the intervention program, a 12-session curriculum (youth and adults) or the control program, a 12-session evidence-based job skills curriculum (youth only), and (3) completes the end of program survey.

The end of the study is defined as completion of the end of program survey shown in the Schedule of Activities (SoA), **Section 1.3**.

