The intervention will be evaluated utilizing all available data from participating youth and adults receiving the SCC curriculum or the control curriculum and completing pre-intervention and/or post-intervention surveys. We recognize retention can be a challenge; our team has experience with maintaining high retention in community intervention studies through a detailed contact sheet collected at baseline, scheduled follow up calls and emails, and working with community partners to help find youth. A system of escalating incentives for youth and adult participants will be employed. Youth will receive \$15 for completing the baseline survey, \$5 for completing each of the 12 feedback sessions, and \$20 for completing the survey after program completion (total \$95). Adults will receive \$15 for completing the baseline survey, \$5 for completing each of the 10 feedback sessions, and \$20 for completing the survey after program completion (total \$85). Even participants who may have missed portions of the sessions will still be asked to complete the post-intervention survey, utilizing an 'intent to treat' design.

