6 STUDY INTERVENTION(S) OR EXPERIMENTAL MANIPULATION(S)

6.1 STUDY INTERVENTION(S) OR EXPERIMENTAL MANIPULATION(S) ADMINISTRATION

6.1.1 STUDY INTERVENTION OR EXPERIMENTAL MANIPULATION DESCRIPTION.

This pilot community-partnered cluster-randomized trial will examine the feasibility and acceptability of a social network-based youth violence prevention program called Strengthening Connections for Change for youth ages 13-17 and their self-identified key adult supports to focus on leadership, strengthening intergenerational networks, community engagement, and violence prevention. The study will be located in four lower resource Pittsburgh, Pennsylvania neighborhoods ('clusters') randomized to receive either the Strengthening Connections for Change program (i.e. intervention neighborhoods) or to a job skills training program (i.e. control neighborhoods). Randomization will occur 1:1 at the site level (2 intervention and 2 control sites). The study team will then work with each community-based site to recruit youth already engaged with the respective community site into the program to which each site has been randomized. The Strengthening Connections for Change intervention will be delivered weekly by research staff in twelve 2-hour sessions at community sites. The first 2 sessions will include youth-specific programming. For session 3-12, youth and adults will participate in separate programming for the first hour, then participate in a joint session.

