9 STATISTICAL CONSIDERATIONS

9.1 STATISTICAL HYPOTHESES

Aim 3: To pilot test the feasibility and acceptability of the adapted YES intervention compared to a control intervention (Job Skills) among adolescents and their key adult supports at four community-based sites.

Approach: Participant tracking and post-intervention surveys will assess feasibility and acceptability.. Exploratory outcomes will include changes between pre-and post-intervention assessments of social network structure, relationship quality, social support (emotional and instrumental), attitudes towards violence, and violence involvement.

Primary Outcome Measure:

1. Participant Attendance: Attendance is recorded at the beginning and end of each session. Calculated as a proportion of total number of sessions attended (possible session attended #: 0-12 for youth participants and 0-10 for adult participants; possible proportion attended range: 0-1). [Time Frame: through intervention completion, 12 weeks]

2. Participant Satisfaction: At the end of the program, participants will be asked about how satisfied they were overall with the topics discussed and format of the program using 5-point Likert scale items. Means score will be calculated across the items (possible range: 1-5; higher score means higher satisfaction). [Time Frame: end of program (12 weeks)]

Secondary Outcome Measure:

3. Participant Satisfaction: At the end of each weekly session, participants will be asked about how satisfied they were with the topics discussed for that session using 5-point Likert scale items. Means score will be calculated (possible range: 1-5; higher score means higher satisfaction). [Time Frame: weekly for 12 weeks]

Other Pre-specified Outcome Measures:

4. Change in social network composition: Participants will complete an abbreviated social network survey that asks them to identify key sources of emotional and instrumental support, and to characterize the nature of these relationships (network size, network density, mean link strength). [Time Frame: Baseline, end of program (12 weeks)]

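### Adult attendance, a primary endpoint, has a maximum of 9 sessions in Sections 1.1 and 3 but 10 in Section 9.1, and the protocol schedules ten adult sessions

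*Combined protocol and SAP*

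**What the plan says.** Feasibility is one of the two primary outcomes. It is calculated for each participant as sessions attended over sessions possible, and is estimated separately for youth and adults (Sections 9.4.1 and 9.4.2). The documents give the adult session count as follows.

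- Section 1.1, Synopsis (Endpoints): "possible session attended #: 0-12 for youth participants and 0-9 for adult participants", with "possible proportion attended range: 0-1".
- Section 3, endpoint table: "0-12 for youth participants and 0-9 for adult participants", with the same 0 to 1 range.
- Section 9.1, primary outcome 1: "0-12 for youth participants and 0-10 for adult participants", again with a 0 to 1 range.
- Section 6.1.1: of the twelve sessions, the first two are for youth only. "For session 3-12, youth and adults will participate in separate programming for the first hour, then participate in a joint session".
- Section 5.5: adults are paid for "completing each of the 10 feedback sessions", with a stated total of 85 dollars.
- Section 4.4: completion for the intervention arm is described in terms of a 12-session programme for both youth and adults.
- Section 4.3: the adapted curriculum first had 9 sessions and was later expanded to 12.

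No passage says which section prevails, and the amendment history in Section 10.4 has no entries.

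**The concern.** The same primary endpoint has two different maxima for adults. The one in the Synopsis and the endpoint table disagrees with the number of sessions adults are scheduled to attend. An analyst who follows Section 3 and one who follows Section 9.1 would report different adult means and intervals from the same sign-in sheets. As the plan stands, that choice could be made after the data are seen.

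The adult component is what distinguishes this programme from its parent curriculum. Section 3 says the pilot should show whether changes are needed before a larger trial. Too small a denominator makes adult attendance look better than it was, and so pushes that decision in the favourable direction.

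**Working it through.** **Inputs.** Total sessions 12, of which the first 2 are for youth only and sessions 3 to 12 include adults (Section 6.1.1). Adult payments are 15 dollars at baseline, 5 dollars per session form and 20 dollars at the end, with a stated total of 85 dollars (Section 5.5). The adult maximum is 9 (Sections 1.1 and 3) or 10 (Section 9.1).

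**Step 1: count the adult sessions.** Sessions 3 to 12 inclusive: 12 − 2 = 10. This reproduces the 10 in Section 9.1 but not the 9 in Sections 1.1 and 3.

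**Step 2: cross-check on the payment schedule.** Total = 15 + 5k + 20 for k paid sessions.

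- k = 9: 15 + 45 + 20 = 80 dollars
- k = 10: 15 + 50 + 20 = 85 dollars (the stated total)
- k = 12: 15 + 60 + 20 = 95 dollars (the youth total)

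The payment line is internally consistent at ten and at neither alternative.

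**Step 3: effect on individual scores.** Proportion = sessions attended / denominator.

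| Sessions attended | Out of 9 | Out of 10 | Difference |
|---|---|---|---|
| 6 | 0.667 | 0.600 | 0.067 |
| 7 | 0.778 | 0.700 | 0.078 |
| 8 | 0.889 | 0.800 | 0.089 |
| 9 | 1.000 | 0.900 | 0.100 |
| 10 | 1.111 | 1.000 | 0.111 |

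The ratio is 10/9 = 1.111 for every non-zero count. Out of 10, the scale runs from 0 to 1 as stated. Out of 9, an adult who attends every session falls outside it.

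**Step 4: effect on the adult mean.** Suppose adults attend 7.5 of ten sessions on average. This figure is illustrative and not from the documents. Out of 10 the mean is 0.75; out of 9 it is 7.5/9 = 0.833. The limits of a confidence interval for the mean scale by the same factor.

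**Step 5: effect on any cut-off.** Section 9.2 refers to the proportion of participants who achieve the feasibility outcome, but the plan states no attendance threshold. Taking thresholds as assumptions:

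- At 75%, an adult with 7 sessions passes out of 9 (0.778) and fails out of 10 (0.700).
- At two-thirds, an adult with 6 sessions passes out of 9 (0.667) and fails out of 10 (0.600).
- At 70%, 80% or 90%, no adult's classification changes.

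**The case against.** The strongest reply is that Sections 1.1 and 3 do not instruct anyone to divide by 9. They give 0 to 9 as the possible count and 0 to 1 as the possible proportion, which is coherent when read alone. A value above 1 appears only when that maximum is combined with the ten sessions in Section 6.1.1, and only for an adult who attends all ten. An analyst would notice it. This is fair as far as it goes. But the documents state no cap and no uncounted session that would make 9 correct, and the less visible error remains: an adult who misses one session is scored as a full attender.

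A second reply is that the consequence is small. Section 9.1, inside the statistical section, already has 10. Only adults in the intervention arm are affected. The analysis is descriptive with no test. Attendance is kept on source sheets, so the proportion can be recalculated. All of this is true and limits the scope. It does not remove a conflict in the definition of a primary endpoint, and separate reporting of adults means that the youth data cannot dilute it.

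Three supporting points deserve less weight. Section 4.4 most likely gives the length of the curriculum and names who takes part, rather than setting twelve as an adult denominator. That the 9 survives from the original nine-session curriculum is a plausible guess that the documents do not confirm. The payment total shows that ten adult feedback payments were intended, but it sums a sentence that already says ten, so it supports Section 6.1.1 without being separate proof.

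**Conclusion.** The concern holds. The adult maximum of 9 in Sections 1.1 and 3 contradicts the 10 in Section 9.1 and does not match the ten adult sessions in Section 6.1.1 or the ten paid forms in Section 5.5. If the endpoint table is followed, every non-zero adult proportion is 11.1% too high in relative terms, by up to 0.11 on the proportion scale, and full attendance scores 1.11.

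This assumes that adults are offered the ten sessions described in Section 6.1.1 and that all ten count towards attendance. Youth attendance (0 to 12) is unaffected, as is the precision statement in Section 9.2 for 25 adolescents per arm. The point should be corrected before analysis because it concerns a primary endpoint.

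**What to change.** Give adult attendance a single denominator, equal to the number of sessions adults are offered in the final curriculum, and state it in the same words in Sections 1.1, 3 and 9.1, with the count running from 0 to that number. Sections 6.1.1 and 5.5 both give ten. If the study team intends that one of those sessions should not count, the plan should say which one and why. In the same edit, add a few words to Section 4.4 to make clear whether its 12 is the length of the curriculum or the number of adult sessions.

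The cost is a change of wording in two or three sections plus the clarification in Section 4.4. No data collection, visit or analysis method changes.

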1.2 SCHEMA

1.3 SCHEDULE OF ACTIVITIES

	Baseline	Session 1-12	EOP
Informed Consent	X		
Research Survey	X		X
Emotional Distress Checklist	X	X	X
Session Feedback Forms		X	
Session Activities		X	
Interview			X
Adverse Events Reporting	X	X	X

2 INTRODUCTION

2.1 STUDY RATIONALE

The overarching goal of this cluster randomized trial is to assess feasibility and acceptability of the Strengthening Connections for Change program. The first component of the study will involve iterative development of the Strengthening Connections for Change intervention with 5 adolescent-adult support dyads at a single community site. The goal of the first component is to identify gaps in the curriculum and obstacles to implementation that can be addressed prior to the RCT. In the pilot cluster-randomized trial, we will assess feasibility and acceptability by tracking recruitment, enrollment, attendance, and post-intervention surveys. We will also collect exploratory data on proposed outcomes to assess the feasibility of this data collection method and provide preliminary insights to guide a larger trial. Pre-intervention surveys will assess social support, social network structure, attitudes towards violence, conflict resolution and coping, future orientation, self-reported violence perpetration and victimization, ethnic identity, discrimination, and substance use. Post-intervention surveys will assess satisfaction and engagement and will reassess social networks, attitudes towards violence, conflict resolution and coping, future orientation, and violence experiences. We will also conduct semi-structured interviews with a subsample of adolescent-adult dyads in the intervention arm to further assess acceptability and guide refinements for a larger effectiveness trial.

2.2 BACKGROUND

Youth violence is pervasive and increases morbidity and mortality. Each year over 500,000 youth seek care in U.S. emergency departments for assault-related injuries. Middle school-age youth in urban environments bear a disproportionate burden of witnessing and directly experiencing violence, with several studies demonstrating upwards of 97% of youth endorsing a lifetime history of community violence exposure, 5% being shot or stabbed, 19% witnessing a shooting or stabbing, and 13% having a weapon pulled on them in the past year. Exposure to pervasive violence can negatively impact physical and mental health and risk behaviors and increases risks for injury and incarceration. Strategies that leverage individual and relational assets to combat youth violence in urban environments during middle adolescence are urgently needed. Adult connection may play a significant role in violence prevention. Supportive adult connections are an important source of social support across adolescence, with the provision of both emotional support (things others do to make one feel loved and cared for) and instrumental support (tangible help that others provide) conferring protection against myriad health risk behaviors, including violence.

Building upon this evidence base, the CDC Center for Injury Prevention and Control recently put forth key prevention strategies for combating youth violence focusing on adolescent-adult connections: “foster safe, stable, nurturing relationships between young people and their parents and caregivers” and “build and maintain positive relationships between young people and caring adults in their community.” Research in low-resource urban populations suggests that families often struggle to protect youth in these contexts, and that the simple presence of an adult support may not universally confer protection from violence. Instead, interactions between youth and multiple social supports may be more important in

understanding risks. Additionally, grounded in social influence theory, researchers suggest that attitudes towards violence among youth's adult supports may play a mediating effect. Failure to fully account for interconnected positive and negative adult influences across contexts could explain previous mixed findings. Interventions that strengthen adolescent-adult support networks offer a novel approach to youth violence prevention.

Despite the importance of adolescent-adult connections, aside from intensive family-focused approaches for chronic offenders, few evidence-based violence prevention programs exist for middle adolescence that foster adolescent-adult relationships. The Youth Empowerment Solutions program (YES), an evidence-based violence prevention program, fosters interactions with adult volunteers and has been shown to reduce aggression and delinquency. In the YES 'building intergenerational partnerships' program component, youth interview and select adult volunteers without preexisting connections to join them in implementing community change projects. While youth report high satisfaction with the intergenerational partnership component, they have also identified challenges in fostering and maintaining meaningful adult connections in a short time span. Social network analysis can better elucidate how networks of adult supports may uniquely confer protection from violence in low-resource urban neighborhoods and identify novel leverage points for intervention.

The Strengthening Connections for Change intervention, an adaptation of YES, uses social network analysis methods to enhance the 'building intergenerational partnerships' component that leverages existing adolescent-adult relationship networks to increase social support and reduce violence perpetration and victimization among youth in urban neighborhoods.

2.3 RISK/BENEFIT ASSESSMENT

2.3.1 KNOWN POTENTIAL RISKS

Since this study is a minimal risk study, there are few risks to participants who take part in the research study. The risks are a potential breach in confidentiality and the potential that some questions in the surveys may have sensitive question topics or be emotionally distressing.

